4.6.4 Subgroup Analyses

Exploratory subgroup analyses using descriptive statistics will be provided for the primary and secondary endpoint change from baseline in WASO at Week 4 and 12 for the following subgroups:

- Average weekly frequency of moderate to severe HF over 14 days prior to respective visit confirmation date for the HF eligibility (<35 moderate to severe HF per week, ≥35 − <50 moderate to severe HF per week, ≥50 moderate to severe HF per week) per actual stratification.
- Region (North America, Europe)
- BMI (<18.5, 18.5 to <25, 25 to <30, ≥ 30 kg/m²)
- WASO as measured by PSG at baseline (quartiles)

If the number of participants is too small (less than 10%) within a subgroup, then the subgroup categories may be redefined prior to unblinding the study.

4.7 Interim Analyses

No interim analysis is planned.

4.8 Changes to Protocol-planned Analyses

In the protocol, Table 1-1 and Table 3-2 specifies that for the ICEs 'temporary study treatment interruption' and 'Intake of prohibited concomitant medication having impact on efficacy' data collected after the ICE will be discarded for the primary estimand. In the SAP, this is updated to clarify that only data collected during the ICE will be discarded (Section 1.1). If an ICE 'temporary study treatment interruption' and/or 'Intake of prohibited concomitant medication having impact on efficacy' occurred during the week 4 timeframe but not for week 12, the updated data handling method would not discard the week 12 assessment.

Version 2.0 Page: 42 of 57

In addition, the definition of the ICE temporary study treatment interruption at week 4 in Section 9.3.1 of the protocol considers week 1 to week 4 for the calculation of treatment taken <80%. The definition was updated to consider week 0 in the calculation as well as including the PSG nights. The 'treatment taken on <5/7 days during either week 3 or 4' was also updated to consider the 7 days prior to the last PSG assessment since the visit may not be performed at the end of week 4. The same update to ICE temporary study treatment interruption at week 12 was implemented.

The MMRM model in Section 9.3.2.2. of the protocol specified that an interaction term baseline-by-week would be included as a covariate in the model. Due to the short treatment period and small sample size of the study, the baseline-by-week interaction term has been removed from the analytical model specified in Section 4.2.2 of the SAP.

A tipping point analysis was specified in the protocol as a sensitivity analysis for the primary estimand. This analysis has been removed from the SAP since this is an estimation study and a meaningful difference has not been established for this population to be used as the threshold to find the tipping point.

5. Sample Size Determination

The primary objective for the study is to estimate the treatment effect of elinzanetant compared to placebo in the change from baseline in WASO to week 4. Therefore, the sample size is based on precision (i.e. the half width of the confidence interval).

There are no data available on the primary endpoint WASO measured by PSG in women with sleep disturbance associated with the menopause. Therefore, the standard deviation used in the sample size calculation is obtained from a study in patients with insomnia disorder (Mignot et al. 2022). Assuming the pooled standard deviation is 33.2 for the change from baseline in WASO at week 4, a total sample size of 70 participants (35 per arm) would give a 90% probability that the 2-sided 90% confidence interval will have a half width of 14.7 minutes or less.

To account for missing data and possible inflation in variability due to missing data imputation, a total of approximately 78 (39 per treatment) will be randomized in a 1:1 ratio to both treatments. Approximately 223 participants will be screened to achieve 78 randomized participants.

Version 2.0 Page: 43 of 57

6. Supporting Documentation

6.1 APPENDIX 1: Population Characteristic

6.1.1 Participant Disposition

The number of participants enrolled, randomized and valid for the FAS, SAF and SLAS will be summarized overall and by study treatment and study site.

The number of participants randomized will further be summarized by country/region and by study treatment and overall.

The number of sites will be summarized by country/region.

The number of participants with important protocol deviations and the number of screen failures will be summarized overall and by study treatment, country/region and study site.

The number of participants per important deviation category and validity finding will be presented by study treatment and overall.

A disposition summary will be presented summarizing the number of participants starting and completing each study period (screening, treatment, follow-up), the number of participants discontinuing it and the primary reason for discontinuation. This will be presented overall and for each study treatment. The number of participants completing the overall study will be provided by study arm and overall. Participants who completed the study are those who complete study treatment and were followed for the duration of the study. Follow-up is considered to be completed if the participants complete the follow-up visit.

6.1.2 Demography and Other Baseline Characteristics

All demographic and baseline characteristics will be summarized using descriptive statistics by study treatment and overall based on the FAS and SLAS.

Demographic and baseline assessments to be summarized will include:

- Age (at inclusion), race, ethnicity
- Age groups (<40 years, 40 49 years, 50 59 years, 60 65 years, > 65 years)
- Weight (kg), height (cm), body mass index (BMI; kg/m²)
- BMI group ($< 18.5, 18.5 \text{ to } < 25, 25 \text{ to } < 30, \ge 30 \text{ kg/m}^2$)
- Smoking history (Never, Former, Current)
- Alcohol substance (abstinent, light, moderate, heavy)
- Caffeine consumption (mg) per day

Daily caffeine consumption will be calculated using data on the Caffeine Consumption eCRF page. The page captures the volume consumed (over a month, week, or day) for each type of caffeine substance (caffeinated coffee, caffeinated tea, energy drink, cola-type beverage, other). The caffeine content for each substance type in the below table will be used as a guide (Mayo Clinic).

Version 2.0 Page: 44 of 57

Table 6-1: Caffeine Content

Substance type	Caffeine amount (mg) per 8 US fl oz
Caffeinated coffee	96
Caffeinated tea	47
Energy drink	72
Cola-type beverage	22
Other	22

For each 'Type of substance' on the eCRF page, follow the below steps:

1. Convert 'Average volume / amount consumed' into a ratio of 8 oz using the conversion table below:

'Unit of average volume / amount consumed'	Conversion factor
oz	oz / 8
mL	(mL x 0.034) / 8
dL	(dL x 3.381) / 8
L	(L x 33.814) / 8

- 2. Multiple by the caffeine amount specified in Table 6-1.
- 3. If 'Per time period' is recorded as 'Every Month', divide by 30.4. Else, if 'Per time period' is recorded as 'Every Week', divide by 7.

To calculate the caffeine consumption per day, sum the amount of caffeine for all types of substance together from step 3.

6.1.3 Reproductive and Menstrual History

Reproductive and menstrual history will include information on number of pregnancies, number of births, years being amenorrheic and number of participants with oophorectomy. Oophorectomy is based on Relevant Prior and Concomitant Procedures and the PTs Hysterosalpingo-oophorectomy, Oophorectomy, Oophorectomy bilateral, Salpingo-oophorectomy, Salpingo-oophorectomy bilateral, Salpingo-oophorectomy unilateral will be used. If the start date of the procedure is incomplete, the following rules will be applied to determine if the procedure is prior:

- If day is missing but the month and year is known, procedure will be prior if the month and year is before the month and year of start of treatment.
- If day and month are missing but year is known, procedure will be prior if the year is before the year of start of treatment.

Version 2.0 Page: 45 of 57

These variables will be analyzed descriptively, separately for each treatment group and overall based on the SAF.

6.1.4 Protocol Deviations

Important deviations from the protocol and validity findings and the resulting assignment of participants to the analysis sets (see Section 3) are agreed upon in the blind review meeting (BRM). The documentation of important deviations, validity findings and the assignment of participant data to analysis sets will be performed according to the sponsor's applicable Standard Operating Procedures and/or Instruction Manuals. The definition for important deviations and validity findings will be provided in the 'Specification of assessment criteria and identification requirements' before unblinding the data.

Identification of important deviations and validity findings will be done periodically while the study is running, concluding with the completion of the final list during the BRM. Any changes to the statistical analysis prompted by the results of BRM will be documented in an amendment and, if applicable, in a supplement to this SAP.

The list of important deviations and validity findings will only be final after assessment of conditional findings, which are validity findings that can only be identified after unblinding of study treatment.

6.1.5 Medical History

Medical history will be tabulated using medical dictionary for regulatory activities (MedDRA; current version at the time of analysis) terms. The number of participants with medical history findings will be presented by primary system organ class and preferred term overall and per study treatment.

6.1.6 Relevant Prior and Concomitant Procedures

Relevant prior and concomitant procedures performed during the study other than those scheduled in the protocol will be tabulated using medical dictionary for regulatory activities (MedDRA; current version at the time of analysis) terms. The number of participants with relevant prior and concomitant procedures findings will be presented by primary system organ class and preferred term overall and per study treatment.

6.1.7 Prior, Concomitant and Post-Treatment Medication

For prior and concomitant medications, the following definitions apply:

- Prior medication: Medication taken before start of the study intervention intake, (regardless of when it ended).
- Concomitant medication: Medication taken during treatment period, i.e., between first and last study intervention intake (regardless of when it started or ended).
- Post-treatment medication: Start of medication is after last study drug intake.

Missing dates will be imputed as described in Section 4.1.1.4.

Prior, concomitant and post-treatment medication will be coded to Anatomical Therapeutic Chemical (ATC) classification codes according to the World Health Organization Drug Dictionary (WHO-DD, current version at the time of analysis). The number of participants taking prior, concomitant, post-treatment medication, and prohibited concomitant medications will be presented by study treatment and overall using ATC classes and subclasses.

Version 2.0 Page: 46 of 57

6.2 APPENDIX 2: Definitions of Sleep Parameters

6.2.1 PSG Endpoints

PSG recordings will be sent to a vendor for central scoring. Files will be scored manually, and sleep parameters will be provided using the definitions in the below table:

Table 6-2: PSG Endpoint Definitions

Parameter	Definition
Wakefulness after sleep onset (WASO)	Minutes of wake from onset of persistent sleep to lights on. Persistent sleep defined as 20 consecutive epochs (10 minutes) on non-wakefulness.
Sleep efficiency (SE)	(Total sleep time / time in bed) x 100.
Latency to persistent sleep (LPS) Duration in minutes from lights off to the first epoch of 20 epochs of non-wakefulness.	
Total sleep time (TST)	Duration of total REM and NREM sleep during time in bed.
Sleep onset latency to N1 (SOLN1)	Duration in minutes from lights off to the first epoch of non-wakefulness (N1, N2, N3, or REM).
Sleep onset latency (SOL)	Duration in minutes from lights off to the first epoch of sleep other than N1 (i.e., N2, N3, or REM).
Wake time during sleep (WTDS)	Minutes of wake from onset of persistent sleep to the last epoch of sleep stage N2, N3 or REM before lights on. That is, does not include "terminal wake" from last epoch of N2, N3, or REM before lights on.
Early morning wake time (EMWT)	Minutes of wake from the last epoch of sleep stage N2, N3 or REM prior lights on to lights on or end of the file.
Total wake time (TWT)	Total wake time from lights off to lights on.
Percentage of TWT	(TWT / time in bed) x 100.
Number of awakenings (NAW)	Count total number of awakenings from onset of persistent sleep to lights on. An awakening is defined as a PSG recording of at least two consecutive wake epochs. An awakening must be separated by an epoch of stage N2 or stage N3 or stage R. Separation by stage N1 does not denote a new awakening.
	Terminal awakening will not be counted. Terminal awakening is the last awakening prior to lights-on and the participant remains awake until lights-on. If participant is asleep at lights-on, there is no terminal awakening.
Mean duration of awakenings	Average of all awakenings after onset of persistent sleep, not including any terminal awakening.
WASO by quarter	Minutes of wake for each quarter, starting from lights off, where each quarter is 2 hours long. If total recording is not 8 hours, then some quarter may not be available.
	If persistent sleep is not achieved by that quarter, then quarter will be reported blank.

Statistical Analysis Plan BAY 3427080 / 22423 Version 2.0

Page: 47 of 57

Stage N1 sleep time	Total duration in minutes in stage N1 from lights off to lights on.
Percentage of stage N1 sleep	(Stage N1 sleep time / TST) x 100.
Stage N2 sleep time	Total duration in minutes in stage N2 from lights off to lights on.
Percentage of stage N2 sleep	(Stage N2 sleep time / TST) x 100.
Stage N3 sleep time	Total duration in minutes in stage N3 from lights off to lights on.
Percentage of stage N3 sleep	(Stage N3 sleep time / TST) x 100.
Non-REM sleep time	Total duration in minutes in non-REM sleep (Stage N1+N2+N3) from lights off to lights on.
Percentage of Non-REM sleep	(Non-REM sleep time / TST) x 100.
REM sleep time	Total duration in minutes in stage REM from lights off to lights on.
Percentage of REM sleep	(REM sleep time / TST) x 100.
REM onset latency from sleep onset	Duration from sleep onset (first epoch of sleep) to the first REM epoch.
Periodic limb movement disorders with arousal index (PLMAI)	Number of PLM with arousal per hour during total sleep time.
Apnea hypopnea index (AHI)	Total count of Apnea and Hypopnea per hour during total sleep time.
Arousal index	An arousal is an abrupt shift in EEG frequency, which may include theta, alpha, and/or frequencies greater than 16 Hz but not spindles. The minimum duration of an arousal event is 3 seconds, with at least 10 seconds of stable sleep preceding the change. Scoring arousals during REM must also be accompanied by a concurrent increase in submental EMG lasting at least 1 second. The index is based on the number of all arousals scored and counted
	during sleep time reported per hour.
Number of stage shifts	Number of stage shifts from stage 2, 3, or REM to stage 1 or Wake from lights off to lights on.

Version 2.0 Page: 48 of 57

6.2.2 Sleepiz One+ Endpoints

The Sleepiz One+ monitoring device will capture and record raw data, which will be processed by the vendor's software to derive the nightly parameters as defined below:

Table 6-3: Sleepiz One+ Endpoint Definitions

Parameter	Definition
Wakefulness after sleep onset (WASO)	Time duration, in minutes, the monitored subject was awake between the sleep onset (first sleep period longer than 10 minutes) and the last awakening.
Sleep efficiency (SE)	Percentage of time the monitored subject is asleep while in bed, from the person's last entry into bed before falling asleep, and the person's last exit from the bed.
Total sleep time (TST)	The total time during the recording where the subject was asleep.
Sleep onset latency (SOL)	Time duration, in minutes, from the person's last entry into bed before falling asleep, to the first sleep event with a duration greater or equal to 10 minutes.
Wake up latency	Time duration, in minutes, between the last transition from asleep to awake to the person exiting the bed for 10 minutes or more.
Awakening count	Number of times the monitored subject woke up between the sleep onset (first sleep period longer than 10 minutes) and the last awakening.
Average awakenings	The average duration of awakenings (in mins)
Out of bed count	Number of times the monitored subject was out of bed (no presence detected) between the sleep onset (first sleep period longer than 10 minutes) and the last awakening.
Time in bed (TIB)	Total time during the recording where the subject was in bed.
Respiratory irregularity index (RII)	The total number of abnormal breathing events (pauses) per hour of sleep, measured via radar. This value is analogous to the apneahypopnea index (AHI).
Heart rate per minute	The minimum, maximum, mean, median,10th and 90th percentile heart rate over the night.
Breathing rate per minute	The minimum, maximum, mean, median,10th and 90th percentile breathing rate over the night.
Good signal duration	Time duration where the subject is in sight of the device and where either movement, breathing rate, or heart rate can be computed.

Version 2.0 Page: 49 of 57

6.3 APPENDIX 3: Identification of Prohibited Medications

Drug groupings, individual drug names and manual review will be used to identify prohibited therapies and medications that were defined in protocol Section 10.7. This includes prior hormonal therapies, medications that affect PK, and medications potentially confounding efficacy that are to be washed out during the screening period as well as the identification of the ICE prohibited concomitant medications impacting efficacy.

The list of prohibited medications together with the pre-defined washout time period for their effect will be reviewed during blind review of the data and finalized prior to unblinding.

Table 6-4: Preliminary list of prohibited hormonal therapies by drug groupings

DGCODEL0	DGNAME0	DGCODEL1	DGNAME1	DGCODEL2	DGNAME2	Impact duration of concomitant medication
		108	Drugs acting on gonadotropin- releasing hormone (GnRH) receptors	109	GnRH agonists	From 1st dose to 12 weeks after the last dose.
		108	Drugs acting on gonadotropin- releasing hormone (GnRH) receptors	110	GnRH antagonists	From 1st dose to 12 weeks after the last dose.
		5	Hormone replacement therapy	2	Oestrogens used in replacement therapy	1, From 1st dose to 4 weeks after the last dose if the route is vaginal, intravaginal, cutaneous, nasal, topical or transdermal. 2, From 1st dose to 8 weeks after the last dose if the route is oral or sublingual. 3, From 1st dose to 12 weeks after the last dose if the route is intramuscular. 4, From 1st dose to 24 weeks after the last dose if the route is sintramuscular. 5, From 1st dose to 24 weeks after the last dose if the route is subcutaneous or intradermal.
		5	Hormone replacement therapy	3	Progestogens used in replacement therapy	1, From 1st dose to 4 weeks after the last dose if the route is vaginal, intravaginal, cutaneous, nasal, topical or transdermal. 2, From 1st dose to 8 weeks after the last dose if the route is oral or sublingual. 3, From 1st dose to 12 weeks after the last dose if the route is subcutaneous or intradermal. 4, From 1st dose to 24 weeks after the last dose if the route is intramuscular.

Version 2.0

DGCODEL0	DGNAME0	DGCODEL1	DGNAME1	DGCODEL2	DGNAME2	Impact duration of concomitant medication
		772	Cancer therapies	738	Endocrine antineoplastic therapy	From 1st dose to 12 weeks after the last dose.

Page: 50 of 57

Table 6-5: Preliminary list of prohibited concomitant medication impacting PK by drug grouping

DGCODEL0	DGNAME0	DGCODEL1	DGNAME1	DGCODEL2	DGNAME2	Impact duration of concomitant medication
45	Drugs interacting with CYP3A	240	CYP3A inducers	225	Moderate CYP3A inducers	From 1st dose to 4 weeks after the last dose Considered not to have an influence on efficacy, if route is auricular(otic), ophthalmic or conjunctival.
45	Drugs interacting with CYP3A	240	CYP3A inducers	265	Strong CYP3A inducers	From 1st dose to 4 weeks after the last dose

All listed drug names in Table 6-6 were reported in NIRVANA as of finalization of this SAP.

Table 6-6: Preliminary list of prohibited concomitant medication potentially confounding efficacy by drug names

WHO Drug Name	WHO Drug Record Number	WHO Drug Sequence Number 1	Impact duration of concomitant medication
DIPHENHYDRAMINE HYDROCHLORIDE	000004	02	From 1 st dose to 2 weeks after the last dose
BETAMETHASONE DIPROPIONATE;BETAMETHASONE SODIUM PHOSPHATE	000085	13	From 1 st dose to 2 weeks after the last dose if route is oral.
DIAZEPAM	000170	01	From 1 st dose to 4 weeks after the last dose
METHOCARBAMOL	000479	01	From 1 st dose to 2 weeks after the last dose
METHYLPREDNISOLONE	000496	01	From 1 st dose to 2 weeks after the last dose if route is oral
HYDROXYZINE	000584	01	From 1 st dose to 2 weeks after the last dose
HYDROXYZINE HYDROCHLORIDE	000584	02	From 1 st dose to 2 weeks after the last dose

Page: 51 of 57

Version 2.0

WHO Drug Name	WHO Drug Record Number	WHO Drug Sequence Number 1	Impact duration of concomitant medication	
CLONIDINE	001711	01	From 1st dose to 2 weeks after the last dose	
CLONAZEPAM	002852	01	From 1 st dose to 4 weeks after the last dose	
CYCLOBENZAPRINE	004284	01	From 1 st dose to 2 weeks after the last dose	
CITALOPRAM	005826	01	From 1st dose to 2 weeks after the last dose	
CITALOPRAM HYDROBROMIDE	005826	02	From 1 st dose to 2 weeks after the last dose	
TRAMADOL	005992	01	From 1 st dose to 2 weeks after the last dose	
TRAMADOL HYDROCHLORIDE	005992	02	From 1 st dose to 2 weeks after the last dose	
BUPROPION HYDROCHLORIDE	007005	02	From 1 st dose to 2 weeks after the last dose	
TIZANIDINE HYDROCHLORIDE	007407	02	From 1 st dose to 2 weeks after the last dose	
CETIRIZINE HYDROCHLORIDE *	008843	02	From 1 st dose to 2 weeks after the last dose if frequency is once daily (QD) or 3 times per week	
LORATADINE *	009175	01	From 1st dose to 2 weeks after the last dose if frequency is once daily (QD) or 3 times per week	
GABAPENTIN	010030	01	From 1st dose to 2 weeks after the last dose	
TOPIRAMATE	012017	01	From 1st dose to 2 weeks after the last dose	
VENLAFAXINE HYDROCHLORIDE	012338	02	From 1st dose to 2 weeks after the last dose	
MELATONIN	012432	01	From 1st dose to 2 weeks after the last dose	
FEXOFENADINE HYDROCHLORIDE *	013142	02	From 1st dose to 2 weeks after the last dose if frequency is once daily (QD) or 3 times per week	
FEXOFENADINE;PSEUDOEPHEDRINE HYDROCHLORIDE *	129590	03	From 1st dose to 2 weeks after the last dose if frequency is once daily (QD) or 3 times per week	
DESLORATADINE *	013985	01	From 1 st dose to 2 weeks after the last dose if	

Page: 52 of 57

Version 2.0

WHO Drug Name	WHO Drug Record Number	WHO Drug Sequence Number 1	Impact duration of concomitant medication
			frequency is once daily (QD) or 3 times per week
LEVOCETIRIZINE DIHYDROCHLORIDE *	015302	02	From 1st dose to 2 weeks after the last dose if frequency is once daily (QD) or 3 times per week
BILASTINE *	071040	01	From 1st dose to 2 weeks after the last dose if frequency is once daily (QD) or 3 times per week
ACTAEA RACEMOSA **	014568	01	From 1 st dose to 2 weeks after the last dose
ACTAEA RACEMOSA EXTRACT **	014568	04	From 1 st dose to 2 weeks after the last dose
ACTAEA RACEMOSA EXTRACT;BORON;CALCIUM;FOLIC ACID;GLYCINE MAX EXTRACT;MAGNOLIA OFFICINALIS;NICOTINIC ACID;PYRIDOXINE HYDROCHLORIDE;RIBOFLAVIN;SELENIUM;THIAMI NE;TOCOPHEROL;VITAMIN B12 NOS **	113355	02	From 1st dose to 2 weeks after the last dose
DOXYLAMINE SUCCINATE	003341	02	From 1 st dose to 2 weeks after the last dose
FEZOLINETANT	093415	01	From 1 st dose to 2 weeks after the last dose
HYDROCODONE	000600	01	From 1 st dose to 2 weeks after the last dose
ALPRAZOLAM	005952	01	From 1 st dose to 2 weeks after the last dose
OXYBUTYNIN	005389	01	From 1 st dose to 2 weeks after the last dose
NIRMATRELVIR;RITONAVIR	158921	01	From 1 st dose to 2 weeks after the last dose
TRIAMCINOLONE ACETONIDE	000319	02	From 1 st dose to 2 weeks after the last dose
PHENTERMINE	001317	01	From 1 st dose to 2 weeks after the last dose

^{*} Non-sedating antihistamines/pseudoephedrine are allowed up to twice per week per protocol. Participants with PRN or 'as needed' are considered as taking these medications according to the study protocol.

^{**}These medications belong in the drug grouping DGNAME2 'Oestrogen used in replacement therapy' and should have impact duration specified in this table instead of the impact duration specified in Table 6-4.

Version 2.0 Page: 53 of 57

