At least 2 weeks or 5 half-lives (whichever is longer) prior to SCR-2 visit	 Antidepressant drugs Anticonvulsants Antipsychotics (for depot neuroleptics consider long half-lives) Anxiolytics (benzodiazepines, non-benzodiazepines) Hypnotics Centrally acting anticholinergics Mood stabilizers Muscle relaxants (centrally acting with psychotropic effects) Central Alpha-2 Receptor Agonists Sodium oxybate Sedating antihistamines Melatonin and melatonin receptor agonists Stimulants Adenosine Receptor Antagonist Systemic corticosteroids (inhaled corticosteroids are allowed) Diet pills that contain active substance and/or ingredients that can affect sleep Isotretinoin Any recreational drugs, even if used for medicinal reasons Opioids/narcotics Over-the-counter (OTC) /herbal treatments including: Supplements with possible psychotropic effect Extended-release pseudoephedrine Traditional Chinese medicine used for sleep improvement/disturbances 	
PSG = polysomnography, S0	CR = Screening.	

21 SEP 2023 Page: 70 of 73

Table 10-5: Medication with limited use during the study

During the study	Therapies
Allowed up to twice per week	 Non-sedating antihistamines. See Table 10–6 for non- sedating antihistamines which are prohibited during the study as CYP3A4 substrates.
	Pseudoephedrine

CYP3A4 = Cytochrome P450 isoenzyme 3A4.

Table 10-6: Prohibited concomitant medication potentially affecting PK.

Washout period before SCR-2	Therapies
At least 2 weeks or 5 half-lives (whichever is longer) prior to SCR-2 visit: CYP3A4 substrates with a narrow therapeutic range	Alfentanil, astemizole, fentanyl, pimozide, terfenadine
At least 2 weeks or 5 half-lives (whichever is longer) prior to SCR-2 visit: Strong or moderate inhibitors of CYP3A4	Nefazodone, fluvoxamine, tofisopam
At least 2 weeks or 5 half-lives (whichever is longer) prior to SCR-2 visit: Strong or moderate inducers of CYP3A4	Carbamazepine, phenytoin, St. John's wort, phenobarbital, primidone
Washout period before BL	Therapies
From 1 week prior to BL visit: CYP3A4 substrates with a narrow therapeutic range	Cisapride, cyclosporine, dihydroergotamine, ergotamine, quinidine, sirolimus, tacrolimus
From 2 weeks prior to BL visit: Strong or moderate inhibitors of CYP3A4	See Table 10–7 for examples of most common moderate and strong CYP3A4 inhibitors
From 4 weeks prior to BL visit: Strong or moderate inducers of CYP3A4	See Table 10–8 for examples of most common moderate and strong CYP3A4 inducers

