6.4.3 Intake of prohibited concomitant medication having impact on efficacy

The list of prohibited concomitant medications that were defined in the protocol to influence efficacy will be finalized prior to unblinding. Missing dates will be imputed as described in Section 4.1.1.4.

PSG assessments during any intake of prohibited medication or intake that occurred prior to the PSG assessment and is within the washout period of the prohibited medication (i.e., within the timeframe specified in the impact duration column of Table 6-4, Table 6-5and Table 6-6) will be considered as an intercurrent event. PSG assessments will be performed on 2 consecutive nights at each visit and if only one of the nights fall within the timeframe, then that night will be discarded while the other night will be included in the analysis. For the identification of this ICE, visit day 30 and day 86 will be used as the PSG assessment day for week 4 and week 12 respectively if PSG assessment(s) are missing. The preliminary list of prohibited concomitant medications are specified in Section 6.3.

Version 2.0 Page: 55 of 57

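### SAP Table 6-6 flags seven non-sedating antihistamine entries only at two named frequencies, so other regimens above the twice-weekly limit would have no intercurrent-event window

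*SAP*

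**What the plan says.** **Protocol, Section 10.7.** Table 10-5 covers non-sedating antihistamines and pseudoephedrine: "Allowed up to twice per week". Table 10-4, the list of prohibited therapies that may affect sleep/wake function, includes "Extended-release pseudoephedrine" with no frequency allowance.

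**SAP, Section 6.3, Table 6-6.** Seven starred entries (cetirizine, loratadine, fexofenadine, fexofenadine/pseudoephedrine, desloratadine, levocetirizine, bilastine) share one conditional impact duration, from the first dose to 2 "weeks after the last dose if frequency is once daily (QD) or 3 times per week". The footnote restates the limit, "Non-sedating antihistamines/pseudoephedrine are allowed up to twice per week per protocol", and adds: "Participants with PRN or 'as needed' are considered as taking these medications according to the study protocol".

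**SAP, Section 6.4.3.** The intercurrent event covers "PSG assessments during any intake of prohibited medication or intake that occurred prior to the PSG assessment" where that earlier intake is still inside the washout. The section explains this as "within the timeframe specified in the impact duration column of Table 6-4" and the two tables that follow it.

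**SAP, Sections 1.1 and 4.2.2.1.** The primary estimand handles prohibited medication by a hypothetical strategy, and only nights inside the event window are discarded.

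**Status of the list.** Table 6-6 is titled preliminary, manual review supplements it, and the list "will be reviewed during blind review of the data and finalized prior to unblinding".

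**The concern.** The limit is a threshold, but Table 6-6 turns it into a match on two frequency codes. A threshold catches everything above it; two codes catch only themselves. The outcome is not ordered by intensity of use. A once-daily user loses PSG nights up to 2 weeks after her last dose, while a twice-daily user dosing on the PSG night itself has no window and is kept. Regimens between the two named codes, such as every other day, are also missed.

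At stake is the match between the retained PSG nights and the primary estimand, which is meant to describe WASO without prohibited medication affecting sleep. Intercurrent-event counts by arm would be too low if unmatched records exist. The same impact durations also decide which baseline data are usable for PROMIS SD SF 8b, ISI, the sleep diary, the HFDD, GAD-7 and PGI-S. Section 4.8 of the SAP, which lists departures from the protocol-planned analyses, does not mention the two-frequency rule.

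**Working it through.** **1. Regimens against the two rules.** Limit: up to 2 per week (protocol Table 10-5, SAP footnote). Rule as written: QD or 3 times per week (SAP Table 6-6).

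| Recorded regimen | Intakes per week | Above the limit? | Window in Table 6-6 as written? |
|---|---|---|---|
| Once weekly | 1 | no | no |
| Twice weekly | 2 | no | no |
| 3 times per week | 3 | yes | yes |
| Every other day | 3.5 | yes | **no** |
| 4, 5 or 6 times per week | 4 to 6 | yes | **no** |
| Once daily (QD) | 7 | yes | yes |
| Twice daily (BID) | 14 | yes | **no** |
| Three times daily (TID) | 21 | yes | **no** |
| PRN | depends on actual intake | unknown | no (footnote) |

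**2. From table to analysis.** Section 6.4.3 ties the event to the impact-duration column. An entry whose condition is not met has no duration, so no event arises. Section 4.2.2.1 discards only nights inside an event window, so the night is retained.

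**3. The plan's precision figure, used here only as a scale.** Inputs (protocol Section 9.5, SAP Section 5): SD 33.2 min, 35 per arm, two-sided 90% CI.

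- Half-width = t(0.95, 68) × s × √(2/35). With s = 33.2 this is 13.23 min.
- With s² distributed as 33.2² × χ²(68)/68, the 90th percentile of the half-width is 14.65 min, and P(half-width ≤ 14.7) = 0.907. With 34 per arm the probability is 0.870.

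The stated 90% probability of 14.7 min or less is reproduced and is not in dispute.

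**4. Illustrative size.** The documents give no count of affected participants and no effect of these drugs on WASO. Assume k = 1 to 3 retained participants, all in one arm, each with a Week 4 mean shifted by D = 10 to 33.2 min (the upper value is one planning SD). Shift in the unadjusted arm mean = k × D / 35.

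- Smallest: 1 × 10 / 35 = 0.29 min, and 0.29 / 14.7 = 2% of the half-width.
- Middle: 2 × 20 / 35 = 1.14 min, or 8%.
- Largest: 3 × 33.2 / 35 = 2.85 min, or 19%.

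**5. Pseudoephedrine, by comparison of passages.** Protocol Table 10-4 names the extended-release form. Table 10-5 allows pseudoephedrine, without naming a form, up to twice per week. SAP Table 6-6 names fexofenadine with pseudoephedrine hydrochloride, states no release form, and applies the frequency condition and the PRN exemption. Whether the row departs from Table 10-4 therefore depends on a product detail that is not given.

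**The case against.** The strongest reply is that this is not yet the final rule. The list is preliminary, manual review is a separate route, and it will be finalised before unblinding. Section 6.4.3 opens by referring to any intake of a prohibited medication, and the footnote states the correct limit, so a careful reviewer could still class twice-daily use as an intercurrent event. That stands as a limit on the claim: exclusion of such records from the event is what the text produces if followed literally, not a certain outcome. It does not supply the missing criterion, however. Manual review has no stated frequency rule, and Section 6.4.3 explains its window by the same column that carries the two codes.

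Second, the list was built from blinded data, and perhaps only these two frequencies had been reported. The SAP says this of the drug names but not of the frequencies. A reader might infer that nights have been wrongly kept, or that the event counts are wrong. The documents do not support that: they show no participant on another regimen, and no use near a Week 4 PSG.

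Third, a reader might infer that the fexofenadine/pseudoephedrine row contradicts protocol Table 10-4. Because the release form is not given and Table 10-5 allows pseudoephedrine twice weekly, a conflict is possible but not established. The SAP also rests on protocol version 2.1 of 06 FEB 2024, whereas the protocol reviewed is Amendment 1 of 21 SEP 2023. The twice-weekly limit is not affected by this, since the SAP repeats it.

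Finally, six of the seven entries are antihistamines that the protocol classes as non-sedating, the trial tests no hypotheses, and the first supplementary estimand keeps all nights on prohibited medication. These points limit the size of the problem, but the primary estimand should still be implemented as defined.

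**Conclusion.** The condition on the seven starred entries does not implement the limit that the SAP itself restates. Applied literally, every-other-day use, 4 to 6 times per week, twice daily and three times daily would escape the intercurrent event, while once-daily use triggers it. This is a mis-stated rule rather than missing detail, and it should be corrected before the list is final.

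The likely effect on the estimate is small: 0.29 to 2.85 min in one arm mean (2% to 19% of the 14.7 min half-width) under the assumed counts and shifts, less if affected participants fall in both arms, and zero if no such records exist. The pseudoephedrine question is a point to reconcile, not a demonstrated contradiction.

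**What to change.** When the list is finalised at blind review, replace the two named frequencies in all seven starred rows with the protocol's own threshold: *if the recorded frequency is more than twice per week*. The threshold should count intakes rather than days, because twice-daily use on two days is four intakes and would pass a rule based on days.

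Separately, establish the release form of the reported fexofenadine/pseudoephedrine product. Check it, together with the PRN exemption, against Tables 10-4 and 10-5 in the protocol version in force, and reconcile the passages before unblinding.

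The cost is an edit to one SAP table and its lookup code. The protocol already requires dose and frequency of concomitant medication to be recorded (Section 6.9). The downside is that a few more PSG nights may be discarded.
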